### 11.2.2 Study Termination

#### 11.2.2.1 Study Termination for Safety Reason

Occurrence of two deaths suggesting a reasonably possible relationship with continuous exposure to emapalumab and occurring in similar conditions will trigger the decision to terminate the study.

This process will involve both the iDMC and the Investigator. The management of patients already enrolled in the study will also be part of the iDMC recommendations.

#### *11.2.2.2 Study Termination for Absence of a Demonstrated Benefit*

The decision to terminate the study due to absence of a demonstrated benefit will be one of the responsibilities of the iDMC, based on the ongoing review of the individual patient data and benefit/risk analysis.

In case of study termination, the management of the patients already enrolled in the study will also be part of the iDMC recommendations.

## **12 STATISTICAL CONSIDERATIONS AND ANALYTICAL PLAN**

Full details of all planned analyses will be specified in separate documents describing PK/PD and Statistical Analyses, which will be finalized prior to the locking of the study database. This section contains an overview of the planned methods of analysis with regard to safety and efficacy variables.

### **12.1 SAMPLE SIZE**

Approximately 12 patients (a minimum of 10 sJIA patients) will be enrolled across North America and Europe. The sample size is based on pragmatic considerations, and on the experience acquired from primary HLH patients treated with emapalumab.

### **12.2 ANALYSIS SETS**

All analysis sets will be defined prior to final database closure. In addition to the analysis sets listed below, further exploratory analyses may be performed using other subgroups of patients.

#### **12.2.1 Safety Analysis Set**

The safety analysis set will include all patients who receive any part of an infusion of study drug.

#### **12.2.2 Intent-to-Treat Analysis Set**

The intent-to-treat (ITT) analysis set will coincide with the Safety Analysis Set.

#### **12.2.3 Per-Protocol Analysis Set**

The per-protocol analysis set will consist of all ITT patients who complete the study without major violations of the study protocol. Detailed listing of major protocol deviations will be defined in the SAP prior to locking of the final database.

### **12.3 STATISTICAL AND ANALYTICAL METHODS**

For measurements of continuous endpoints, summary statistics will include n, mean, median, standard deviation, minimum and maximum values. For binary data (proportions of patients showing a defined variable) the numbers and percentages will be tabulated.

All study variables are considered to be exploratory in this study, and no hierarchy of endpoints has been specified, as the objective of this pilot study is to confirm that the proposed dose regimen is adequate in this patient population.

Analysis will focus on descriptive statistics and confidence intervals. As this is a pilot study, statistical methods will focus on summarizing the data collected using descriptive statistics and on appropriate graphical presentations.

### 12.3.1 Efficacy Data

Graphical and tabular summaries will be prepared for each of the MAS distinct features, e.g. *fever; splenomegaly; WBC; platelet counts; liver function test (in particular ALT/AST); fibrinogen; ferritin; LDH.*

For binary endpoints (MAS remission by Week 8, number of patients who taper glucocorticoids, number of patients who discontinue due to lack of efficacy), 95% confidence intervals will be calculated for proportions.

For time to event endpoints (time to MAS remission, time to achievement of glucocorticoids tapering and time to death), Kaplan-Meier curves will be calculated and summary statistics, such as medians, proportions event-free at various time points will be calculated and presented, and 95% confidence intervals calculated where possible.

### 12.3.2 Safety Data

All data relating to safety will be listed and summarized using descriptive statistics.

AEs will be coded and tabulated by body system, and by individual events within each body system. AEs will also be tabulated by severity and relationship to the study medication. Summaries will also be produced of SAEs and AEs leading to withdrawal from the study.

For each clinical laboratory test, individual patient values will be listed and summarized and change from pre-treatment baseline values calculated and summarized. Summaries of marked abnormalities and shift tables will be tabulated for each laboratory test.

In addition, other exploratory analyses of safety data, including summaries for different subsets of patients, may be conducted.

### 12.3.3 Pharmacodynamic Data

All PD data will be summarized using appropriate graphical and tabular presentations.

Exploratory statistical models will be fitted, and correlation analyses undertaken, to investigate the relationships between PD data and clinical measures of response. ROC curves may be used to summarize any relationships that are found.

In addition, other exploratory analyses of pharmacodynamic endpoints, including summaries for different subsets of patients, may be conducted.

### 12.3.4 Immunogenicity Data

The numbers of patients with anti-drug antibodies present at each assessment point will be summarized.

### 12.3.5 Missing Data

No imputations of missing data will be performed. However, the following rules will be applied to ensure that all patients can be included in the final analysis:

- patients who are withdrawn from the study prior to Week 8 because of safety concerns or poor efficacy will be classified as non-responders from the time of their withdrawal in all

analyses of response status, and their data will be censored at time of withdrawal in all time-to-event analyses. For continuous endpoints in such patients, all analyses for time points beyond the point of withdrawal will exclude missing data for these patients.

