## 6.5 RESCUE THERAPY

Patients who are withdrawn from the study due to a safety issue or for lack of efficacy (i.e. worsening of MAS/no response to emapalumab) will be treated according to the standard of care at the site.

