## 7.4 EFFICACY ENDPOINTS

The efficacy of emapalumab in this patient population will be evaluated based on the evolution of the MAS distinct features of cytopenias, liver function and coagulopathy.

In particular the following variables will be assessed:

- Number of patients achieving MAS remission by Week 8 after initiation of emapalumab treatment.
- Time to MAS remission.
- Number of patients for whom at any time during the study glucocorticoids can be tapered *i)* to the same (or lower) dose being administered before the occurrence of MAS (in those patients who are already treated for sJIA/AOSD) or *ii)* by 50% (or less) of the dose administered at emapalumab treatment start (in those patients who present with MAS at sJIA/AOSD onset).
- Time to achievement of glucocorticoids tapering (as defined above).
- Survival time.
- Number of patients withdrawn from the study due to lack of efficacy.

MAS remission is defined as

- ✓ Resolution of clinical signs and symptoms according to the Investigator and
- ✓ Normalization of laboratory parameters relevant to MAS, as follows:
  - WBC and platelet count above LLN
  - LDH below 1.5 ULN
  - ALT/AST below 1.5 ULN
  - fibrinogen higher than 100 mg/dL
  - ferritin levels decreased by at least 80% from values at screening or baseline (whichever is higher) or below 2000 ng/ml, whichever is lower.

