Most of the patients are expected to have already received at least glucocorticoid treatments as well as having possibly been previously treated by sJIA specific therapies, some of them for a relatively long time depending on the duration of their underlying rheumatic disease; therefore they may carry variable degree of toxicities caused by those treatments. The data collected to date in pHLH patients who have been heavily pretreated by immune-chemotherapy show that administration of emapalumab does not aggravate toxicities of previous therapies while showing, in general, a favorable impact on HLH activity.

All information collected on disease severity and previous treatments will be taken into account for the analysis of adverse events.

Toxicities of concomitant treatments, authorized or recommended during the administration of emapalumab, may also potentially expose the patients to adverse events; however their benefits may outweigh their risks. No safety concern related to the concomitant administration of emapalumab with other treatments (e.g., antimicrobial agents, anti-hypertensive drugs) has been reported so far. Corticosteroids have already been administered with anti-IFN $\gamma$  therapy in Crohn's Disease without any particular safety concerns (Reinisch W 2010). Of interest, tapering of glucocorticoids had no impact on safety and tolerability of emapalumab infusions and has shown benefit for patients with steroids-related hypertension and generalized immunosuppression.

Although the risk that the emapalumab treatment will not be able to control the disease may exist, the close monitoring and the stopping rules of the study ensure that, in this event, emapalumab treatment will be discontinued and the patients will rapidly receive rescue treatments according to the standard clinical practice at the participating sites. The risks of administering alternate therapy after having received emapalumab seems to be low, since no particular safety concerns were observed during treatment with emapalumab.

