**AND**

2. is a life-threatening event.

*11.1.2.2 All other related SAEs will be judged by the iDMC on a case-by-case basis taking into account the disease evolution (such as signs of improvement in HLH) and the possibility of managing the SAE and ensuring that no patient is exposed to unnecessary risks. Treatment Discontinuation for Lack of Efficacy*

A patient should be discontinued from study treatment for lack of efficacy in the event of any of the followings:

- Rapid worsening of MAS representing immediate risk for the patient and requiring the use of a salvage therapy.
- No Response to emapalumab, provided that there is evidence of IFN $\gamma$  neutralization.

However, upon request by the Investigator to continue emapalumab treatment in the absence of therapeutic alternatives, the iDMC can authorize it after a thorough review of the patient's data and confirmation of lack of risks for the patient.

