## 8. Efficacy Analysis

## 8.1. Efficacy Analysis

The following binary efficacy endpoints will be described using counts, proportions, and exact Clopper-Person 95% CI:

- Patients achieving MAS remission by Week 8 after initiation of emapalumab treatment
- Patients for whom at any time during the study glucocorticoids can be tapered
- Patients who tapered steroids to ≤1 mg/kg/day of prednisone equivalent dose
- Patients withdrawn from the study due to lack of efficacy

The following time-to-event efficacy endpoints will be analyzed descriptively:

- Time to first MAS remission
- Time to achievement of permanent glucocorticoids tapering
- Survival time

Summaries will include for each observed time, the survival estimate, failure rate, number of events and the number of patients remaining, also called population at risk. The median, lower quartile and upper quartile estimates of time-to-event and their 95% CI will be tabulated in a separate table. A Kaplan–Meier graph will be presented for each time-to-event endpoint.

The efficacy analysis will be based on the All Treated Population. Efficacy analyses will be repeated for the EVAL Population.

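### Failure handling is tied to leaving the study rather than stopping emapalumab, so a remission after salvage could be counted if the patient stays in follow-up; and censoring efficacy withdrawals is informative.

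*Protocol*

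**What the plan says.** **Rules that act on leaving the study.** Protocol 12.3.5 states that "patients who are withdrawn from the study prior to Week 8 because of safety concerns or poor efficacy will be classified as non-responders", with effect from the withdrawal date, and adds that "their data will be censored at time of withdrawal in all time-to-event analyses". The efficacy endpoint in Protocol 7.4 is "Number of patients withdrawn from the study due to lack of efficacy"; SAP 2.2.2 repeats it and SAP 8.1 lists "Patients withdrawn from the study due to lack of efficacy". Protocol 12.3.1 words the same endpoint as "number of patients who discontinue due to lack of efficacy", without saying whether treatment or study is meant.

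**Rules that act on stopping treatment.** Protocol 11.1.2.2 states: "A patient should be discontinued from study treatment for lack of efficacy in the event of any of the followings". One of its two triggers is rapid worsening that needs salvage therapy. Protocol 10.5.2.2 says that if the disease is not controlled, "emapalumab treatment will be discontinued and the patients will rapidly receive rescue treatments".

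**Follow-up and other agents.** Protocol 3.4 has every treated patient monitored after the last infusion, normally to SD56. Protocol 6.3.4 bars etoposide and other biologics, with listed exceptions, only while emapalumab is being given. Where treatment is shortened because of remission, SAP 3.1 keeps the patient on the visit schedule to SD56. It has no matching sentence for a stop because of failure.

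**Remission in the SAP.** SAP 6.1.7 counts Week 8 remission when the criteria are met at SD56 ± 5 days, and time to remission as the first date on which they are met. Patients who never meet them are censored at last contact. Neither definition depends on whether emapalumab was stopped or another agent started. The readable part of the SAP Errata entry on MAS remission adds no such condition, though its text is cut off. SAP 6.1.4 does not repeat the protocol's non-responder rule, and SAP section 11 does not list it, or the censoring, as changed.

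**The concern.** Two separate problems follow.

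First, stopping emapalumab for failure and leaving the study are different events here, and only the second makes a patient a non-responder. A patient stopped for failure, treated with something else and still followed could contribute a remission that belongs to the other treatment. The same patient would be absent from the lack-of-efficacy count. The remission proportion would then be too high as a description of emapalumab, and the failure count too low.

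Second, and with no assumption about salvage, a patient withdrawn for poor efficacy is a non-responder for response status but is censored for time to remission. Censoring assumes that the patient would have gone on to remit at the same rate as those still under observation. Someone removed because the drug was not working is the clearest case where that fails, and the error raises the cumulative remission curve.

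**Working it through.** The plan states no power, target rate or calculated sample size to reproduce: about 12 patients is a pragmatic number (Protocol 12.1, SAP 3.2). The check therefore sets the rules side by side and sizes the effect on assumed counts.

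**Step 1: follow one patient through the rules.** Emapalumab is stopped for lack of efficacy under Protocol 11.1.2.2 and another agent is started.
- *If the patient is withdrawn from the study:* Protocol 12.3.5 makes the patient a non-responder, and the lack-of-efficacy endpoint counts the patient.
- *If the patient stays in follow-up (Protocol 3.4) and does not remit:* not a remission, but also not in the lack-of-efficacy count.
- *If the patient stays in follow-up and meets every criterion:* a time-to-remission event, and a Week 8 remission if the criteria are met at SD56 ± 5 days. Again not in the lack-of-efficacy count.

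Only the third path changes the remission figures.

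**Step 2: size for the Week 8 proportion.** One patient is 1/12 = 8.3 points. SAP 8.1 uses exact Clopper-Pearson limits: the lower is the 2.5% quantile of Beta(x, n − x + 1), the upper the 97.5% quantile of Beta(x + 1, n − x). Assume 8 of 12 remissions are reported.

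| Reported remissions that followed salvage | Supplementary remission (95% CI) | Added row: emapalumab stopped for lack of efficacy (95% CI) |
|---|---|---|
| 0 | 8/12 = 66.7% (34.9 to 90.1) | 0/12 = 0% (0 to 26.5) |
| 1 | 7/12 = 58.3% (27.7 to 84.8) | 1/12 = 8.3% (0.2 to 38.5) |
| 2 | 6/12 = 50.0% (21.1 to 78.9) | 2/12 = 16.7% (2.1 to 48.4) |

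The last column assumes no other stops for failure. The study-withdrawal endpoint would show 0/12 in all three rows.

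**Step 3: size for time to remission.** Assumed data, N = 12, with the first infusion as day 1 as in SAP 6.1.7, so SD56 is day 57 and SD56 + 5 is day 62. Seven patients remit on days 14, 18, 21, 24, 28, 35 and 49. Four never remit and are censored on day 57. One stops for failure on day 15. Cumulative remission is 1 − S, where S is the Kaplan-Meier estimate.
- *Followed, salvaged, remits on day 43:* 8 events and no earlier censoring, so 1 − 4/12 = 66.7%.
- *Withdrawn and censored on day 15 (Protocol 12.3.5):* S = 11/12 after day 14; 10 remain at risk and 6 of them remit. S = 11/12 × 4/10 = 0.367, so 63.3%.
- *Withdrawn and censored at a last contact on day 17 (SAP 6.1.7 with a prompt withdrawal visit under Protocol 8.9):* no event falls between days 15 and 17, so again 63.3%.
- *No event, at risk to day 57 or day 62:* 7 events in 12, so 58.3%.

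The last figure equals the proportion 7/12 that the non-responder rule itself gives. Both censoring rules exceed it by 5.0 points.

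**The case against.** **Failing patients may be meant to leave the study.** Protocol 6.5, the only rescue section, concerns "Patients who are withdrawn from the study due to a safety issue or for lack of efficacy (i.e. worsening of MAS/no response to emapalumab"), and those two descriptions match the triggers in 11.1.2.2. Protocol 11.1.1 also attaches alternative treatment to withdrawal, and Protocol 12.3.1 uses its looser wording for the same endpoint as 7.4. On that reading the non-responder rule already covers these patients. This stands as a plausible intention, but 6.5 describes care for patients who are withdrawn and does not require withdrawal, while 3.4 and 11.1.2.2 point the other way.

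**Counting observed status is a legitimate choice.** The non-responder rule sits under missing data, and a followed patient has data. Reporting remission whatever treatment follows is a recognised treatment-policy approach. This also stands, which is why the as-observed result should be kept. What remains is that the choice is not stated.

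**A case could be traced.** MAS worsening must be reported as an AE (Protocol 10.3.1), and TEAEs leading to treatment discontinuation and concomitant biologics are tabulated (SAP 9.1.1 and 9.6). Patient profiles (SAP 12.1) and the remission and exposure listings in the post-hoc plan give patient-level detail, and the EVAL population (SAP 5) may exclude patients with influential deviations. With about 12 patients these help, but non-response without worsening need not appear as an AE, and none of them alters the All Treated remission figure.

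**The two documents' censoring dates differ.** A reader might infer that this discrepancy moves the result. It does not in the example: both give 63.3%. They would differ only if someone else remitted between withdrawal and last contact. The problem is censoring at either date.

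**Conclusion.** The gap is in the text. Failure handling depends on study withdrawal, while the stopping rule acts on treatment, and the SAP remission definitions carry no condition on salvage.

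A reader might infer that any patient stopped for failure and salvaged counts as a Week 8 remission, or that the reported rate is biased. The documents do not support either. The patient must stay in follow-up and then meet every clinical and laboratory criterion, within SD56 ± 5 days for the Week 8 endpoint; failed salvage is still non-remission. How many patients meet these conditions is unknown and may be none. Each would move the proportion by 8.3 points at N = 12.

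The censoring point needs no salvage assumption, only a patient withdrawn for poor efficacy: 63.3% against 58.3% in the assumed example. It is also inconsistent with the protocol's own classification of that patient as a non-responder.

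The study is descriptive and every endpoint exploratory (SAP 4.1), so no error rate is affected. The change should be made, but at the low end of that priority.

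**What to change.** 1. **Reconcile the passages.** Protocol 3.4, 6.5, 10.5.2.2, 11.1.1, 11.1.2.2, 12.3.1 and 12.3.5 should agree on whether stopping emapalumab for lack of efficacy also means study withdrawal. No clinical rule is proposed here.
2. **Use one rule for time to MAS remission.** Patients withdrawn for poor efficacy have no event and stay at risk to the end of the Week 8 window (SD56 + 5 days). Carry the non-responder classification of Protocol 12.3.5 into SAP 6.1.7, and declare the departure from the protocol's censoring in SAP section 11.
3. **Add a supplementary analysis and keep the as-observed endpoints.** In Tables 14.2.1, 14.2.2.1 and 14.2.2.2, add remission by Week 8 and time to first remission with patients treated as non-responders from the date they stop emapalumab for lack of efficacy, or newly start after the first infusion an agent on a pre-written list. The list should cover etoposide and other biologics and state how newly started cyclosporine and anakinra are handled. Anakinra for an adjudicated sJIA/AOSD flare under Protocol 6.3.1 can be kept apart. It is an analysis list, not a treatment rule.
4. **Add a row to Table 14.2.1** for emapalumab discontinued for lack of efficacy, beside the study-withdrawal row.

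Label the additions post hoc if the database is locked.

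**Cost.** SAP wording, a declared change and a few table rows; patient care is unchanged. Starts of listed agents come from concomitant-medication data, and the SAP Errata already derives daily doses of etoposide, tocilizumab, canakinumab, anakinra and ciclosporin to the end of the study. The reason for stopping emapalumab is harder: the documents show a reason for early study termination (SAP 7.1) and the action taken for each AE (Protocol 10.3.1), but no field for treatment stopped for lack of efficacy. It may have to be established at the data review meeting. The supplementary figure may be less favourable; if no case exists, it confirms the as-observed proportion.

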• by at least 50% of the equivalent dose of prednisone administered at emapalumab treatment start (in those patients who present with MAS at sJIA/AOSD onset).

The daily equivalent dose of prednisone will be compared with the daily equivalent dose of prednisone at SD0.

AD-ST-33.04 Effective date: 30-Jun-2017

Version 2.0 | Date 29-Oct-2020 | AD-PR-109.01 Effective date: 26-Jun-2017

Page 23 of 51

If it is not possible to establish if a patient has been treated for sJIA/AOSD or not before study start for all patients, or if it is not possible to retrieve glucocorticoids dose administered before the occurrence of MAS for all patients who already are treated for sJIA/AOSD, the glucocorticoids tapering endpoint will be changed. In this case the endpoint will be: "glucocorticoids permanently tapered at any time during the study by at least 50% of the equivalent dose of prednisone administered at emapalumab treatment start (SD0).

If glucocorticoid dosing data are unavailable at a given time point, the assumption that dose has not been further tapered from the previous available observation will be made. Glucocorticoid doses will be calculated as (prednisone-equivalent) mg/kg/day.

- MAS remission = resolution of clinical signs and symptoms according to the Investigator (MAS clinical signs and symptoms score ≤ 1) AND normalization of laboratory parameter relevant to MAS as follows:
  - White blood cell count (WBC) and platelet count above the lower limit of normal (LLN)
  - Lactate dehydrogenase (LDH) below 1.5 upper limit of normal (ULN)
  - Alanine aminotransferase/aspartate aminotransferase (ALT/AST) below 1.5 ULN
  - Fibrogen higher than 100 mg/dL
  - Ferritin level decreased by at least 80% from values at screening or baseline (whichever is higher) or below 2000 ng/mL, whichever is lower

If one or more laboratory data are unavailable within the visit window, the LOCF approach will be used.

- MAS remission by week 8 = patients who meet MAS remission conditions in the period SD56  $\pm$  5 days regardless the time of first MAS remission or its duration.
- Survival:

Time to death = date of death - date of first emapalumab infusion + 1

Patients who survive to the end of the study will be censored at the date of last contact. In case in which a patient withdrew consent the censoring date will be the date of withdrawal of consent.

• Time to MAS remission:

AD-ST-33.04 Effective date: 30-Jun-2017

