Version 2.0 | Date 29-Oct-2020 | AD-PR-109.01 Effective date: 26-Jun-2017

Page 24 of 51

date of first MAS remission – date of first emapalumab infusion + 1

Time to the first MAS remission will be calculated from the date of first emapalumab infusion until the date of first MAS remission. Patients who do not meet the criteria of MAS remission will be censored at the date of last contact.

The MAS remission evaluation is based on a combination of assessments, including Investigator assessment and laboratory findings. The latest date of assessments, within the visit window of  $\pm$  3 days around the planned day of the visit, will be used for the calculation of the time to MAS remission.

• Time to achievement of permanent glucocorticoids tapering:

date of glucocorticoids tapering – date of first emapalumab infusion + 1

Time to achievement of glucocorticoids tapering will be calculated from the date of first emapalumab infusion until the date in which the target level of glucocorticoid dose reduction is permanently achieved. Patients who do not meet the criteria of glucocorticoids tapering will be censored at the date of last contact.

• The total daily dose of anakinra, canakinumab, ciclosporin, etoposide, methotrexate, and tocilizumab will be calculated for each subject using the same unit of measurement provided in the concomitant medication log.

Total daily dose = dose \* Number of doses per day

Where the number of doses per day are derived using the same approach for the calculation of the equivalent dose of prednisone equivalent.

• Glucocorticoids tapering to  $\leq 1$  mg/kg/day of the equivalent dose of prednisone:

Achievement of permanent glucocorticoids tapering and last equivalent dose of prednisone is  $\leq 1$  mg/kg/day.

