## 11. Changes from Planned Analysis

The Safety analysis set coincides with the All Treated Population and it is not listed in the analysis populations section. The EVAL Population has been added to check the robustness of the efficacy results. The Per-Protocol analysis set has been removed due to the small sample size and the introduction of the EVAL population.

Infusion-related reaction has been added in the safety endpoints (Section 2.2.1).

AD-ST-33.04 Effective date: 30-Jun-2017

Version 2.0 | Date 29-Oct-2020 | AD-PR-109.01 Effective date: 26-Jun-2017

The glucocorticoids tapering endpoint has been modified when it is not possible to establish whether a patient have been treated for sJIA/AOSD or not before study start for all patients or when it is not possible to retrieve glucocorticoids dose administered before the occurrence of MAS for all patients who already are treated for sJIA/AOSD. In this case the endpoint is "Number of patients for whom, at any time during the study, glucocorticoids can be tapered by 50% (or more) of the dose administered at emapalumab treatment start.

IL-10, sCD163, TNFa and IL-18 may be analysed and/or reported separately.

The following have been added:

- safety patient profile reports (Section 12.1)
- descriptive summaries of neutralizing antibody in case of positive ADA results (Section 9.5.3)
- Number and percentage of patients who tapered steroids to  $\leq 1 \text{mg/kg/day}$  of the equivalent dose of prednisone (Section 6.1.7)

No other changes from the analyses specified in the protocol are planned.

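### Time to remission and time to tapering censor the failures, so one minus Kaplan-Meier can exceed the share of patients who achieve the event, and the protocol and SAP give different censoring dates

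*Protocol*

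**What the plan says.** Protocol 12.3.5 has a rule in two halves for patients withdrawn from the study before Week 8 because of safety or poor efficacy. In analyses of response status they are non-responders from withdrawal onward. In the time-to-event analyses, "their data will be censored at time of withdrawal in all time-to-event analyses".

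SAP 6.1.7 sets its own rule for each endpoint. For remission: "Patients who do not meet the criteria of MAS remission will be censored at the date of last contact". For tapering: "Patients who do not meet the criteria of glucocorticoids tapering will be censored at the date of last contact". Neither sentence makes an exception for a patient who dies or is withdrawn as a failure, so by their general wording a death without the event is censored too. For survival the SAP adds a further date: "In case in which a patient withdrew consent the censoring date will be the date of withdrawal of consent".

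SAP 8.1 then reports, in the All Treated Population, the survival estimate and the failure rate at each observed time, and adds: "The median, lower quartile and upper quartile estimates of time-to-event and their 95% CI will be tabulated in a separate table". The outputs are Tables 14.2.2.1 to 14.2.3.2 and Figures 14.2.6 and 14.2.7. Neither document names a competing-event method. SAP 11 lists the departures from the protocol, does not mention the change of censoring date, and closes with "No other changes from the analyses specified in the protocol are planned".

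**The concern.** Censoring in Kaplan-Meier assumes that the patient who leaves has the same later chance of the event as those who stay. That is not credible for these patients. A patient who dies can no longer remit or taper. A patient withdrawn for failure is already treated by the plan as an outcome in three ways:

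- as a non-responder (Protocol 12.3.5);
- as a patient who is not replaced (Protocol 12.5.1, SAP 6.1.4);
- when the cause is lack of efficacy, as an efficacy endpoint in its own right (Protocol 7.4).

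The consequence is descriptive. The event-free estimates, quartiles and curves can show a larger share remitting or tapering than did so, and can report a quartile that was never reached. Everything is declared exploratory (Protocol 12.3, SAP 4.1), so no type I error or power is involved. In a single-arm study of this size, though, the description is the result, and SAP 1 foresees its use in submissions and manuscripts.

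The point is limited to deaths and to withdrawal from the study, which Protocol 6.5 foresees: "Patients who are withdrawn from the study due to a safety issue or for lack of efficacy". A patient who only stops the drug and stays in follow-up (Protocol 3.4) would be censored near SD56 under the SAP and is not affected.

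**Working it through.** **Inputs.** The plan has no figure to reproduce. Sample size, Protocol 12.1: "Approximately 12 patients (a minimum of 10 sJIA patients) will be enrolled across North America and Europe". I take N = 12. The documents give neither the number nor the timing of failures, so both are assumed. Two patients without remission are followed to day 57 (SD56 on the SAP's scale, which adds 1). The remaining patients either fail (die or are withdrawn as failures, number f) or remit.

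**Formulas.** Kaplan-Meier: S(t) = product over event days of (1 − d/r), where d is the number of events and r the number at risk; the reported failure rate is 1 − S. The comparator is Aalen-Johansen cumulative incidence with failure as a competing event. With no other early censoring it equals the observed share, and equals the result of keeping failures at risk to day 57.

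**Three failures, seven remissions (days 10, 13, 16, 19, 23, 29, 43).** Observed share 7/12 = 58.3%.

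- Failures on days 5, 7, 9: nine remain and seven remit, so 1 − S = 7/9 = 77.8%.
- Failures on days 12, 18, 28: S = 11/12 × (9/10 × 8/9) × (6/7 × 5/6) × (3/4 × 2/3) = 0.262, so 1 − S = 73.8%.
- Failures on days 45, 48, 50: S = 5/12, so 1 − S = 58.3%, no excess.

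**All cases, failures censored on the day they occur.**

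| Failures | Remissions | Observed share | Failures early | Interleaved | Late |
|---|---|---|---|---|---|
| 1 | 9 | 75.0% | 81.8% | 81.0% | 75.0% |
| 2 | 8 | 66.7% | 80.0% | 77.8% | 66.7% |
| 3 | 7 | 58.3% | 77.8% | 73.8% | 58.3% |

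For f = 2 the remissions are on days 10, 13, 16, 19, 23, 29, 36, 43 and the failures on days 7, 9 (early), 14, 24 (interleaved) or 45, 50 (late). For f = 1 a remission on day 40 is added and the failure is on day 7, 20 or 50.

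**Upper limit.** If all f failures precede the first event and nothing else is censored early, e events give e/(12 − f) instead of e/12. The ratio is 12/(12 − f): 1.09, 1.20 and 1.33 for f = 1, 2, 3.

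**Quantiles.** With two interleaved failures, S = 10/12 × 6/9 × 2/5 = 0.222 on day 43, so the upper quartile is reported as day 43 although only 66.7% remit and it is not reached. The median moves only in the early cases with two or three failures (day 23 instead of 29); interleaved it stays at 29.

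**Effect of the censoring date alone.** Two patients withdrawn on day 10, two completers without remission, eight remissions on days 8, 15, 19, 22, 26, 28, 35, 42; observed share 8/12 = 66.7%.

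| Censored | 1 − S |
|---|---|
| At withdrawal | 11/12 × 2/9 = 0.204, so 79.6% |
| 14 days later | 8/12 × 2/6 = 0.222, so 77.8% |
| 30 days later | 5/12 × 2/3 = 0.278, so 72.2% |
| 46 days later | 4/12 = 0.333, so 66.7% |

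**The case against.** The strongest objection is that the tables follow the SAP, and the SAP censors at last contact, not on the day of failure. That date reduces the distortion. In the early three-failure case, last contact 28 days after each failure gives S = 6/12 × 2/3 = 1/3, so 66.7% rather than 77.8%, against 58.3%. Protocol 3.4 requires at least four weeks of follow-up after the last dose, and Protocol 8.9 follows withdrawals for a serious adverse event to resolution or a stable outcome. This stands, and the larger figures should be read as applying to deaths, to the protocol's rule, and to patients whose contact ends at withdrawal. It reduces the problem without removing it, and it shows that the choice of date changes the answer.

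Second, withdrawal from the study for failure may be uncommon: Protocol 11.1.2 speaks of stopping study treatment, and three failures by day 9 is an extreme case. That is fair. The interleaved cases are less extreme and still show an excess.

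Third, withdrawal does not make remission impossible, and a patient withdrawn for safety may be improving, so treating it as a competing event is an estimand choice. That is also right; only death strictly precludes the event. The choice does match the non-responder and no-replacement rules, but it needs to be stated.

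Fourth, the SAP also gives numbers at risk, binary proportions and patient listings, so a careful reader could recount. That mitigates the problem but does not make the tabulated failure rates or quartiles correct.

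Finally, the SAP errata revise the assessment-date paragraph for remission. The replacement text is incomplete in the copy reviewed, but the sentence shown as replaced is not the censoring sentence.

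**Conclusion.** The concern holds. As written, the rules censor patients whom the plan itself regards as failures and, by general wording, patients who die. One minus Kaplan-Meier for remission and tapering can then exceed the proportion of treated patients who achieve the event. It does so whenever such a patient leaves the risk set before a later event, and not otherwise. In the 12-patient illustrations with failures censored on the day they occur, the excess ranges from none to 6.8 points for one failure (81.8 − 75.0), 13.3 for two (80.0 − 66.7) and 19.4 for three (7/9 − 7/12 = 7/36). Those sizes rest on assumed numbers and timings, and later last contact makes them smaller.

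The date mismatch is a separate defect: withdrawal in Protocol 12.3.5, last contact in SAP 6.1.7, with no entry in SAP 11. The dates can coincide for a given patient but need not. This censoring does not affect the Week 8 remission proportion, which is defined by status at SD56 ± 5 days. For survival time, ordinary censoring is appropriate.

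**What to change.** For time to MAS remission and time to tapering, report Aalen-Johansen cumulative incidence with death and withdrawal from the study for safety or lack of efficacy as competing events. Alternatively, keep these patients in the risk set without the event to the end of planned follow-up. The SAP should name one, because the two agree only when nothing else is censored early. In the early three-failure case, if one of the two non-remitters is instead an unrelated withdrawal on day 12, cumulative incidence is 65.5%, kept-at-risk 63.3% and one minus Kaplan-Meier 87.3%. If a hypothetical estimand is wanted for failure-withdrawals, the SAP should say so and keep the present rule under that label.

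Keep ordinary censoring for unrelated withdrawals and for survival time. State explicitly how deaths are handled, use one censoring date in Protocol 12.3.5 and SAP 6.1.7, and record the change in SAP 11.

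The cost is SAP wording and a few lines of code, with no new data. The reported remission and tapering probabilities may be lower.
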